- Unilateral transfemoral amputee
- Medicare Functional Classification Level K2 or K3
- Currently using NMPK prosthesis
- Current NMPK prosthesis is well fitting at the socket
- No current stump problems, such as skin breakdown
- Able to ambulate without a gait aid

Exclusion Criteria:

- Previous neuromuscular complications currently affecting gait
- Currently undergoing dialysis treatments
- Amputation of the contralateral limb
- Poor fit of current NMPK prosthesis

Will a Certificate of Confidentiality be obtained? If yes, provide an explanation. No.

Study Design

Methods: Describe, in detail, the research activities that will be conducted under this protocol:

The study design is a reversal design whereby only the prosthetic knee joint will be changed. Each subject will be tested using their current NMPK, fit and tested with a MPK, and then tested again with their NMPK, e.g. A-B-A design. MPK prostheses from all manufacturers will be considered appropriate for testing. Each MPK to be used in this study is FDA approved. Each subject will be given an acclimation period (typically ~4 months) consistent with other similar studies (Hafner, *Archives of Physical Medicine and Rehabilitation*. 88(2):207-217, 2007; Kahle, *Journal of Rehabilitation Research and Development*. 45(1):1-14, 2008; Kaufman, *Archives of Physical Medicine and Rehabilitation Research and Development*. 45(1):1-14, 2008; Kaufman, *Archives of Physical Medicine and Rehabilitation Research and Development*. 46(3): 417-433, 2009) before testing is commenced on the MPK. The foot will be in the L5981 class, e.g. flex foot or equivalent. The same socket, suspension, and foot will be used throughout the study in order to eliminate these confounding variables. All prosthesis fittings will be performed by the subject's own certified prosthetist according to manufacturers' fitting guidelines.

Patient Function (Efficacy): Field based measurements will be obtained using ActiGraph activity monitors attached to waist, and bilaterally to the ankle and thigh for a period of 4 consecutive days, including 2 weekdays and 2 weekend days. The subject will don the monitors in the morning after waking and remove them prior to sleeping.

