characteristic or code that can be used to link the identity of the subject to the		
data		
Dates: All elements of dates [month, day, and year] directly related to an	Х	
individual. Their birth date, date of death, date of diagnosis, etc.		
Note: Recording a year only is not a unique identifier.		
Medical device identifiers and serial numbers		
Biometric identifiers, including finger and voice prints, full face photographic		

images and any comparable images		
Web Universal Resource Locators (URLs), Internet Protocol (IP) address		
numbers, email address		
Street address, city, county, precinct, zip code, and their equivalent geocodes	Х	
Phone or fax numbers	Х	
Account, member, certificate or professional license numbers, health		
beneficiary numbers		
Vehicle identifiers and serial numbers, including license plate numbers		
If None of the above identifiers will be recorded or maintained in the	None	None
dataset and/or sent outside of the study team, please check "None".		

Statistical Information

Note: Power analyses and study endpoints are not needed for a pilot or feasibility studies.

No statistical information. *If checked, please explain*: Statistical Considerations

Power Statement: The study power is based on an effect-size approach (Cohen, *Psychological Bulletin*. 112:155-159, 1992). Based on a paired design with 50 subjects enrolled, there will be 80% power to detect differences in means between the two devices (MPK vs. NMPK) of at least 0.56 standard deviations, which is considered to be a medium effect size. This sample size is larger than previous MPK studies (Hafner, *Archives of Physical Medicine and Rehabilitation*. 88(2):207-217, 2007; Kahle, *Journal of Rehabilitation Research and Development*. 45(1):1-14, 2008; Kaufman, *Archives of Physical Medicine and Rehabilitation*. 87(7): 1382-1385, 2008), where the number of subjects ranged from 15 to 21.

Data Analysis Plan:

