The purpose of this study is to compare the functional efficacy, patient satisfaction, and safety of two prosthesis designs: MPK vs. NMPK. The effects of these two prosthesis designs on these outcome variables will be evaluated using a one-factor repeated measures ANOVA. If the data are not sufficiently Gaussian, a non-parametric procedure such as Friedman's test will be used. Comparisons of A1 versus B, and A2 versus B will be also conducted using multiple comparison procedures or contrasts following the global ANOVA or Friedman's test. All procedures and analysis methods proposed in this study have been used previously and have been thoroughly validated.

The tri-axial accelerometer signals will be processed to yield activity levels of none, low, medium and high. Statistical analysis will determine if there are differences in activity level between the two prosthetic designs. Post-hoc analyses will be performed to determine which activity subscales differ between the prosthetic designs. Asymmetry between the prosthetic and non-prosthetic limb will be quantified using the asymmetry index described by Kaufman et al (Kaufman, *Journal of Pediatric Orthopedics*. 16(2):144-150, 1996). Variations in cadence will be quantified, since the data suggests that K2 patients benefit from a MPK (Theeven, *Journal of Rehabilitation Medicine*. 43(10):906-915, 2011; Burnfield, *Prosthetics and Orthotics International*. 36(1):95-104, 2012). Age related changes in gait will also be quantified.

The SF-36 will be used to determine if quality of life improves with a MPK. A multivariate approach will be used to compare all PEQ subscales simultaneously. If the overall test is significant, post-hoc analyses will be performed to determine which subscales differ between prosthetic designs. The PEQ-A will be grouped according to subject matter content (concentration, confidence, stumbles, falls) and tested to determine if there are differences due to prosthetic design. The information about falls from the biweekly fall tracking mailers will be compiled and compared across prosthesis type (MPK vs. NMPK). The Patient-Specific Functional Scale scores will be compared across time points as well.

Endpoints

Primary: Complete data collection of all subjects and complete statistical analyses Secondary: Manuscript publication

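### Complete-block tests are named for an A1-B-A2 design with no rule for a subject without A2, so by default that subject's A1 and B data are lost from A1 versus B

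*Combined protocol and SAP*

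**What the plan says.** Under Study Design, Methods, the order of phases is fixed: "Each subject will be tested using their current NMPK, fit and tested with a MPK, and then tested again with their NMPK". These phases are A1, B and A2.

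The Data Analysis Plan says that the effects of the two designs on the outcome variables "will be evaluated using a one-factor repeated measures ANOVA". If the data are not close enough to Gaussian, "a non-parametric procedure such as Friedman's test will be used". Comparisons of A1 with B and of A2 with B then follow the global test, by contrasts or multiple-comparison procedures. The Prosthesis Evaluation Questionnaire has its own test: "A multivariate approach will be used to compare all PEQ subscales simultaneously". Falls from the mailers are to be compared by prosthesis type, with no method named.

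The Power Statement reads "Based on a paired design with 50 subjects enrolled", and "there will be 80% power to detect differences in means between the two devices" (MPK and NMPK) "of at least 0.56 standard deviations, which is considered to be a medium effect size".

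The protocol gives no analysis set, missing-data method, dropout allowance or rule for a subject who does not complete A2. The figure of 75 under Target accrual is a screening margin. Complete data collection appears under Endpoints as a goal, which does not say what happens when it is missed.

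**The concern.** Classical repeated-measures ANOVA and Friedman's test work on complete blocks. A subject seen in A1 and B but not in A2 has no complete block, so contrasts taken from such a fit lose two valid measurements that bear directly on the device comparison.

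The design makes this more than a routine missing-data remark. The third phase takes the knee under test away and returns the subject to the old one. It is plausible, though the documents do not discuss it, that willingness to go on depends on how much better the subject did in B than in A1, which is the quantity to be estimated. Complete-case analysis would then condition A1 versus B on an event related to its own result. All materials also travel by mail, so some missing phases are realistic whatever the reason.

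**Working it through.** **1. The plan's own figure.** Inputs from the Power Statement: n = 50, difference 0.56 SD, power 80%. Alpha is not stated; two-sided 0.05 is assumed.

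Power = Φ(0.56/√(2/50) − 1.96) = Φ(2.80 − 1.96) = Φ(0.84) = 80%.

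The stated figure is reproduced, on the scale of the outcome SD with zero within-subject correlation. If 0.56 were in SDs of the paired difference, power would be 97.3%. That is a separate matter, and this point does not depend on it.

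**2. Loss unrelated to outcome.** The same formula with complete cases only, at an assumed 10%, 20% and 30% loss:

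- n = 45: Φ(2.66 − 1.96) = 75.7%
- n = 40: Φ(2.50 − 1.96) = 70.7%
- n = 35: Φ(2.34 − 1.96) = 64.9%

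There is no bias in this case.

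**3. What the named methods do.** Take 50 subjects and remove 10 A2 values, leaving 150 − 10 = 140 observations. A standard repeated-measures ANOVA routine stops because the data are unbalanced. A standard Friedman routine returns no result unless the 10 subjects are deleted. A mixed model uses all 140.

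**4. Loss related to benefit.** Assumed: outcome SD 1, residual SD 0.6 per phase, mean device effect 0.40, SD of the effect between subjects 0.5. Then SD(B − A1) = √(0.6² + 0.6² + 0.5²) = √0.97 = 0.985, and 0.40/0.985 = 0.406. A paired t test on 50 pairs then has about 80% power, and on 40 pairs about 71%.

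Let z = (B − A1 − 0.40)/0.985, and let the chance of missing A2 be p(z) = 1/(1 + exp(−(b + s·z))), with b set to give the assumed loss and s the log-odds per SD of B − A1. Then

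complete-case B − A1 = 0.40 + 0.985 × E[z | A2 observed],

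where E[z | A2 observed] = ∫ z(1 − p(z))φ(z)dz / (1 − loss). At 20% loss:

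| s | E[z given A2 observed] | Complete-case B − A1 | Bias |
|---|---|---|---|
| 0 | 0 | 0.40 | none |
| 0.25 | −0.0495 | 0.351 | −12% |
| 0.5 | −0.0962 | 0.305 | −24% |
| 1 | −0.1732 | 0.229 | −43% |

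With s = 1, the estimate is 0.311 at 10% loss and 0.151 at 30%. In simulation with s = 1 and 20% loss, power for A1 versus B is about 34% to 36%, against about 80% with all pairs, and complete-case B − A2 is 0.29. With all A1-B pairs, or a likelihood estimate on all observed phases, both contrasts return 0.40. With no true effect and 20% loss, rejection is about 7%, 9% and 22% at s = 0.25, 0.5 and 1. At s = 1 almost all rejections are false findings that the MPK is worse.

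**5. The plan's 0.56 as the true effect.** With SD 1, correlation 0.5 and s = 1, complete-case B − A1 is 0.47, 0.39 and 0.31 at 10%, 20% and 30% loss (−16%, −31%, −45%). At 20% loss the bias is −44% with correlation 0 and −24% with correlation 0.7. Using all observed A1 and B values gives 0.56 throughout.

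**The case against.** A reader might infer that the plan excludes subjects without A2 from A1 versus B. It does not say so. Multiple-comparison procedures could include paired tests on every A1-B pair, and Friedman's test is offered only as an example. This stands. What remains is that the default behaviour of the named methods is exclusion, and that the plan leaves the choice open until the data are in.

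A reader might also extend the point to the questionnaire subscales. The multivariate approach is not specified, and nothing shows that it needs all three phases. Falls from the mailers have no named method either. The point therefore rests on the ANOVA and Friedman's test.

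The strongest objection is that bias is conditional. The documents mention no refusal to return to the NMPK, and loss unrelated to benefit causes none. The size depends on assumptions: at s = 0.25 the bias is modest, and dropout driven by satisfaction need not follow accelerometer activity closely. The fall in power to about a third belongs to one strong setting. With a true effect of 0.56 and the variances of step 4, s = 1 and 20% loss leave an estimate of 0.39 and power of about 72%. All this stands, and is why the result is given as a range.

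Finally, a mixed model does not cure everything. Subjects who stop during A2 because they are doing badly on the NMPK are lost for reasons tied to unobserved A2 scores, and the model does not remove that bias.

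**Conclusion.** The concern holds as a conditional one. The plan names complete-block methods for a three-phase design and gives no rule for a subject without A2, so by default valid A1 and B data are lost. Loss unrelated to benefit costs power only, about 80% to 71% at 20% loss. Loss that rises with benefit pulls A1 versus B toward no difference: at 20% loss and a true effect of 0.40, to about 0.35, 0.30 or 0.23 as the dependence goes from weak to strong. If poor responders left instead, the effect would be overstated. Loss rates, variances and strength of dependence are all assumed. The documents do not support the claim that the device effect will be biased, only that the plan leaves it unprotected where protection is easy.

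**What to change.** - Replace the one-factor repeated-measures ANOVA with a linear mixed model: phase (A1, B, A2) as fixed effect, unstructured within-subject covariance, all observed phases included. Take A1 versus B and A2 versus B from this model.
- State that a subject without A2 stays in the A1 versus B analysis.
- For clearly non-Gaussian outcomes, use a signed-rank test on all available A1-B pairs. When loss is confined to A2, the available A2-B pairs are the completers only, so a signed-rank test there keeps the same selection. Specify a model-based or multiply imputed estimate for that contrast.
- Name the multivariate method for the questionnaire subscales and apply the same all-available-data principle to it.
- Add a sensitivity analysis for non-return that depends on unobserved A2 scores, for example by shifting the imputed A2 values over a stated range.

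The cost is plan wording and standard software, with no new data. With complete data the model estimates the same phase differences. The small downside is that it assumes missingness is explained by the observed A1 and B scores, which is why the sensitivity analysis is needed.
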